13.5 Secondary Objectives, Endpoints, Analysis Plans

We will attempt to understand the mechanism of action of exemestane on the primary endpoint of the study. More specifically, we will assess the effects of exemestane on the secondary endpoint biomarkers to see whether the effects of different doses on the primary endpoint is through the secondary endpoint biomarkers or independent of them. This will entail exploratory analysis of the primary endpoint by the secondary endpoint biomarkers while accounting for the effect of treatment.

Secondary objectives:

- To assess safety and toxicity.
- To support the preventive activity of exemestane we will investigate the change in Ki-67 and PgR level on the tumor adjacent intraepithelial neoplasia and/or grossly benign tissue.
- To assess possible association of estradiol level with tissue and circulating biomarkers.
- To investigate possible pharmacogenetic markers.
- To assess drug levels on tissue samples.
- To investigate tissue and circulating proteomics profiling.

Secondary endpoints:

- Exemestane safety and toxicity will be evaluated at the clinic visit according to the Common Terminology Criteria for Adverse Events v4.0 (CTCAE) and by a self-administered Quality of Life questionnaire (MENQOL).
- Change in Ki-67 expression comparing pre-treatment versus post-treatment specimen to compare the antiproliferative effect among the different dosages.
- Serum drug measurements of exemestane and 17-dihydroxyexemestane at the end of treatment.
- Additional validated method of estradiol measurement. This method has a lower detection limit (1 pg/ml) than the CLIA certified estradiol test (Quest) and will serve as a quality control since it has proven to more effectively detect estradiol concentrations at the very low level, which is characteristic of older postmenopausal women.
- Serum concentrations of estrone, estrone-sulfate, will be measured by LC-MS/MS while androstenedione and testosterone will be measured at baseline and at surgery. Sex hormone binding globulin serum levels will be measured by a chemiluminescent microparticle immunoassay (CMIA) on the ARCHITECT *i* System (Abbott Laboratories, Weisbaden, Germany).
- Change in concentrations of insulin, glucose (HOMA index) and lipid profile (total cholesterol, HDL cholesterol and triglycerides) will be evaluated.
- Adipokines: change in leptin and adiponectin serum concentrations will be analyzed and compared among the different treatments arms. These measurements will be performed by the use of commercially available enzyme linked immunoassays purchased from R&D systems (SPACE Import-Export Srl, Milan, Italy).
- Measurement of breast estradiol concentration in tumor and normal breast tissue at time of surgery.
- Centralized evaluation of ER, PgR, Her2 expression in tumor comparing pre-treatment levels (tru-cut biopsy) to post-treatment level expression (surgical specimen). Centralized evaluation of Ki-67 in adjacent intraepithelial neoplasia and or grossly benign tissue.
- Drug measurements of exemestane and 17-dihydroxyexemestane on frozen tissue samples, when available.
- Proteomic analysis will be performed with the new Fusion Tribrid mass spectrometer in [name] Shared Resource for the Herbert Irving Comprehensive Cancer Center (HICCC) at CUMC.
- To analyze the UGT2B17 gene we will use Taqman copy number variation assay (Life Technologies, Monza, Italy).
- Crown like structures in mammary fat tissue by IHC (CD68), comparing pre-treatment (tru-cut biopsy) versus post-treatment (surgical specimens).

Analysis plan

We will present full distributions and median values of circulating biomarkers, Ki-67, exemestane and 17-dihydroxyexemestane in tissue at baseline, after treatment and also of changes and percentage changes (with interquartile ranges) of all continuous variable, by arms. ANCOVA models will evaluate the associations of post values (after treatment) and changes from baseline by study arms adjusting for baseline values, explanatory variables and possible confounders (such as age and BMI). Normal distribution of residuals from full models will be checked and, if needed, a transformation will be considered.

For binary variables, when we need to assess differences in frequencies, Chi-squares tests and Odds ratios (ORs) will be calculated. Multivariate logistic models will be considered to assess differences between

arms, adjusting for possible confounders. We will report nominal P-values and we will highlight associations that meet a false discovery rate adjusted P less than or equal to .05 by the Benjamini and Hochberg method.

Analyses on secondary endpoints will be considered as exploratory since we will not have enough power to draw definitive conclusions.

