2. BACKGROUND

2.1 Breast Cancer

Breast cancer is the most common cancer in women and its incidence is rapidly increasing, largely because of an ageing population and several lifestyle changes, such as decreases in physical activity, increase in obesity, later age at first childbirth, and reductions in breastfeeding. Estrogen is a key factor in breast cancer carcinogenesis, and reductions in its synthesis can decrease breast cancer risk. Estrogen production is driven by the aromatase enzyme, which converts androgens to estrogens. Trials in the adjuvant setting have shown that aromatase inhibitors effectively prevent breast cancer recurrence (1) and breast cancer events in at-risk women (2,3).

The pre-surgical - window of opportunity - trial design has been successfully used to streamline drug development, check tumor sensitivity to a given drug and shape up new preventive strategies (4). The change in Ki-67 labeling index is considered an appropriate endpoint biomarker for preoperative studies (5,6). The post-treatment tumor expression of Ki-67 has been shown to be correlated with disease-free survival and overall survival (7). In addition the Ki-67 analysis on adjacent IEN or atypical hyperplasia can assess the potential preventive activity of the tested agent (8,9).

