However we might expect that an AI would achieve low acceptability similar to the SERMs by high risk women for the undesirable symptoms, bone density loss, musculoskeletal ache, climacteric syndrome, and ultimate possible impact on QoL, significantly compromising their motivation and adherence to a preventive treatment. Therefore, a significant step forward to promote breast cancer prevention in postmenopausal women is to ameliorate QoL issues by seeking for the minimally active AI dose and an intermittent schedule. A lighter schedule, compared to the standard regimen, may be much more appealing to a healthy at-risk woman.

For this purpose we are proposing a pre-surgical phase IIb, randomized, double-blind, multi-center study for postmenopausal women with histologically confirmed ER-positive breast cancer (Stage 0-II) comparing the exemestane standard daily dose regimen versus two alternative, less frequent dose regimens.

Rationale for Biomarkers

Estradiol: Overall, a strong positive association between breast cancer risk and circulating levels of

estrogens is now well confirmed among postmenopausal women; the top 20% hormone levels versus bottom 20% have a two- to three-fold higher risk of breast cancer (17). Interestingly, circulating estradiol levels can predict risk of hormone receptor positive breast cancer for up to 16-20 years. Top versus bottom quartile contrast RR was 2.0 (95% CI: 1.4-2.7; p trend<0.001) for <10 years, 2.0 (95%CI: 1.3-3.1; p trend=0.002) for >10-20 years before diagnosis (18).

The direct consequence of AIs in postmenopausal women is a steep decrease in circulating estrogens and their metabolites. For the assessment of exemestane activity at different doses and schedules the most appropriate biomarker appears to be circulating estradiol concentrations (19-21). In postmenopausal women, estradiol levels are low and their assessment is technically challenging as routine labs generally lack standardized sensitive methods. During estrogen suppression with AIs for breast cancer treatment and prevention, the accuracy of estradiol assay becomes of paramount importance as plasma levels are very low (<5 pmol/L). Liquid chromatography coupled with tandem mass spectrometry (LC-MS/MS) provides greater sensitivity and specificity than radio immunoassays (RIA).

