Ki-67: Several studies indicate that staining with the Ki-67 antibody may be useful in monitoring response to anti-estrogen therapy. We previously conducted a presurgical trial assessing tamoxifen dose escalation. Our study showed that the effects of tamoxifen on breast cancer cell proliferation, as assessed by the change in the percentage of cells expressing Ki-67, was comparable among women who received a daily tamoxifen dose of 1 mg, 5 mg, or 20 mg administered for 4 weeks (22). These results led us to focus on low dose tamoxifen in several chemoprevention trials. Ki-67 proliferation index has hence increasingly been used as a surrogate endpoint. Additional evidences from neoadjuvant trials pointed to a prognostic value of Ki-67. Measurements of tumor Ki-67 level after only 2 weeks treatment with either tamoxifen or anastrozole or their combination improved the prediction of recurrence-free survival over baseline Ki-67 after a median of 3 years in postmenopausal women (6,23).

Our findings on standard and low dose tamoxifen confirmed this observation, Ki-67 expression after 4 weeks of tamoxifen predicted recurrence-free and overall survival significantly better than baseline Ki-67. Post-tamoxifen Ki-67 point increase predicted a 5% significant increased risk of breast cancer recurrence. Likewise, overall mortality, mostly due to breast cancer, was better predicted by post-tamoxifen Ki-67 (7).

More recently, we conducted a WOP trial in postmenopausal women with exemestane (25 mg/day) demonstrating a significant reduction in Ki-67 (a 10 point decrease) without any significant toxicity(24). To support the hypothesis of an alternative dose, the Ki-67 was reduced at the same extent irrespective of time since last drug intake (≤ 24 hours or >24 hours) and serum concentrations of exemestane (10 nM vs 2 nM), according to time since last drug intake (25).

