Progesterone Receptor (PgR): Compared to Ki-67 the role of PgR is less clear, at least with tamoxifen treatment (26). Its modulation by tamoxifen is controversial, some studies showed no significant effect on PgR expression. In a low percentage of participants a decreased expression after short tamoxifen treatment has been observed, and these participants showed a worse response to the treatment, but the data were more informative if both pre and post treatment PgR expression was taken into account (27). Moreover, this receptor may change in time also with no treatment. Similarly to Ki-67 exemestane can significantly reduce PgR expression after 6 weeks of treatment (24). It will be useful to compare the modulating effect by exemestane dose and eventually correlate it to Ki-67 changes.

Sex Hormones: Similarly to estradiol, other circulating sex hormones are involved in breast carcinogenesis, and their analysis can contribute to a better understanding of their role in the tumor pathogenesis and drug efficacy through their modulation. Among postmenopausal women, higher levels of endogenous sex hormones and lower levels of sex hormone binding globulin (SHBG) are associated with increased risk of breast cancer. Literature data clearly show the AIs activity on these hormones is due to the direct enzyme inactivation. We have recently published data in premenopausal women that

showed in a multivariable analysis that SHBG had an HR = 2.26 (95 %CI 1.04-4.89) for the lowest versus the highest tertile (28). Endocrine effects of exemestane standard treatment in postmenopausal breast cancer patients result in suppression of estrone, estradiol and estrone sulfate and lowering of SHBG levels, and it increases testosterone, DHEAS and FSH levels. In this study it will be useful to compare the modulation of such hormones to evaluate the drug activity at different schedules. Their evaluation may help to understand the activity of the different proposed doses, and eventually provide an indication to response prediction (19,29,30).

Insulin – Insulin resistance: There is evidence of an association of androgen excess and insulin resistance, glucose intolerance and dyslipidemia in animal models as well as in women. Insulin resistance is considered an important feature of the metabolic syndrome, and is a risk factor for cardiovascular diseases, type 2 diabetes and cancer (31,32).

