In aromatase deficient mice, in association with the increased levels of androgens, increased abdominal adiposity and higher insulin levels has been described. Several polymorphisms of the aromatase gene CYP19 (rs1008805, rs2446405 and rs2414096) are associated with increased risk for insulin sensitivity and diabetes in African Americans, Caucasians and Japanese(33). Based on these observations, we will measure insulin, glucose levels and insulin sensitivity (HOMA) to assess whether there is a different effect among the three exemestane doses.

Lipid profile: A concern with the use of aromatase inhibitors relates to an increased risk of cardiovascular events. It has been reported that, in postmenopausal women, the increase in cardiovascular risk may be ascribed to changes in lipid metabolism and, above all, to the elevation of low-density lipoprotein (LDL) cholesterol. Amongst aromatase inhibitors, exemestane may potentially have a more neutral effect on circulating lipid changes compared to letrozole and anastrozole. After 6 weeks treatment of exemestane (24), total and HDL cholesterol decreased by -10 mg/dL (IQR -21 to -2) and -7 mg/dL (IQR -14 to -2), respectively. Triglycerides were reduced by -8 mg/dL (IQR -28 to -9). Similar results were previously described, however associated with an increase in LDL-cholesterol(34,35). Based on these observations, we will measure total, LDL,HDL cholesterol and triglyceride levels to assess whether there is a different effect among the three exemestane doses.

Adipokines: In the global picture of breast carcinogenesis, adipose tissue has been shown to play an important role. In particular, two adipokines, leptin and adiponectin, have been studied as risk biomarkers for breast cancer associated with obesity in postmenopausal breast cancer patients. Leptin may influence breast cancer through enhancing expression of aromatase providing a link between body weight (adipose tissue), estrogen levels and the risk for breast cancer development as well as poor prognosis (36). Adiponectin appears to have anti-inflammatory, antiatherogenic, anti-angiogenic and anti-diabetic properties. Serum adiponectin levels are reduced in obese women and they increase after relevant weight loss. Low levels of adiponectin are also closely linked to insulin resistance and hyperinsulinemia, which were demonstrated to be positively associated with breast cancer risk (37).

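### Section 13.5's exploratory mechanism analysis treats every secondary biomarker as a possible mediator of the dose effect on estradiol, which reverses the path for Ki-67 and PgR and duplicates it for the other estradiol measures

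*Combined protocol and SAP*

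**What the plan says.** Section 13.5 opens with a mechanism aim: to look at the secondary biomarkers "to see whether the effects of different doses on the primary endpoint is through the secondary endpoint biomarkers or independent of them". The method given is "exploratory analysis of the primary endpoint by the secondary endpoint biomarkers while accounting for the effect of treatment". No equation is written. The natural reading is a regression of percentage change in estradiol on study arm and a biomarker. No biomarker is excluded, and the endpoint list that follows includes Ki-67, PgR, a second estradiol assay, tissue estradiol, drug levels, adipokines, UGT2B17 genotype and crown-like structures.

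The background describes how the drug acts:

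- Section 2.1: "Estrogen production is driven by the aromatase enzyme, which converts androgens to estrogens".
- Section 2.3, on estradiol: "The direct consequence of AIs in postmenopausal women is a steep decrease in circulating estrogens and their metabolites".
- Section 2.3, on Ki-67: "staining with the Ki-67 antibody may be useful in monitoring response to anti-estrogen therapy".
- Section 2.3, on PgR: "exemestane can significantly reduce PgR expression after 6 weeks of treatment".

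Some listed markers do sit before estradiol or on the exposure path. Section 13.5 includes "Serum drug measurements of exemestane and 17-dihydroxyexemestane at the end of treatment", and Section 2.3 says "Leptin may influence breast cancer through enhancing expression of aromatase".

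**The concern.** A mediator has to lie between treatment and outcome. In the protocol's own account exemestane inactivates aromatase, estrogens fall as the direct result, and Ki-67 is used to monitor the response. Nothing in the documents describes tumour Ki-67 or PgR as lowering serum estradiol. Timing points the same way. Under Sections 3 and 7.5 the final biomarker blood is drawn on the day of surgery or the day before, and the on-treatment tissue is taken at surgery. The supposed mediator is therefore measured with or after the outcome.

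If a less frequent schedule really does suppress estradiol less, adjusting for a consequence of estradiol assigns part of that shortfall to the marker. The report could then say that some of the schedule effect runs through Ki-67, and could give a distorted figure for the remainder. This is bias, not imprecision. More participants would not remove it, and neither would the false discovery rate step in Section 13.5.

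**Working it through.** **The plan's own figure.** Inputs from Section 13.4: margin 6 points, SD 11, one-sided 0.025, 80% power, true difference 0. Then n = 2 × (1.960 + 0.842)² × 11² / 6² = 52.8, so 53 per arm against the stated 54. The t-test power at 54 is 80.2%, and 54 / 0.9 = 60 randomized per arm. The sample size reproduces, and no biomarker enters it.

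**Set-up for the mechanism model.** Let A be the arm (0 daily, 1 less frequent), E the percentage change in estradiol, and M a marker scaled to within-arm SD 1.

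- E = δA + e, with SD 11. Positive δ means less suppression on the reduced schedule.
- M = (r/11)E + cA + u, where r is the within-arm correlation of E and M, and c is any effect of schedule on the marker that bypasses estradiol.
- Regressing E on A and M gives the arm coefficient δ(1 − r²) − 11·r·c.

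The documents give neither r nor c; both are assumed here and shown over a range.

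**Pure chain (c = 0).** The coefficient is δ(1 − r²):

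| Assumed r | 1 − r² | True 10 appears as | True 6 appears as |
|---|---|---|---|
| 0.3 | 0.91 | 9.1 | 5.46 |
| 0.5 | 0.75 | 7.5 | 4.50 |
| 0.7 | 0.51 | 5.1 | 3.06 |

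Simulation with 54 per arm and 20,000 runs per setting gave means of 9.08, 7.50 and 5.09 for a true 10, and 5.46, 4.49 and 3.07 for a true 6. Without the marker in the model, the true difference was recovered. In this chain none of the dose effect on estradiol passes through M.

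**Schedule also acts on the marker directly.** With δ = 6 and r = 0.5 the coefficient is 4.5 − 5.5c:

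- c = −0.8 gives 8.9
- c = −0.5 gives 7.25
- c = −0.27 gives 6.0
- c = +0.5 gives 1.75
- c = +0.8 gives 0.1

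Simulation (5,000 runs each) gave 8.93, 7.22, 5.98, 1.73 and 0.12. The direction of the bias is therefore not fixed.

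**Second serum estradiol assay.** If it shifts by the same δ and has the same within-arm variance, adjusting for it leaves δ(1 − r). At an assumed r of 0.9, a true 10 becomes 10 × 0.1 = 1.0. Estradiol would be said to act through estradiol.

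**The case against.** The strongest reply is that this is one sentence about exploratory work. It names no marker, and it is reasonable for part of the list. That reply limits the point in several ways.

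- **Scope.** A reader might infer that every secondary biomarker is on the wrong side of the model. The documents do not support that. Drug and metabolite levels are plausible mediators. Section 2.3 links leptin and crown-like structures to aromatase expression, so they may be upstream. Removing the clause would discard its valid use.
- **Primary result.** Because 5.1 is below 6, a reader might infer a threat to the non-inferiority conclusion. There is none. The primary model in Section 13.4 names baseline estradiol, BMI, age and time since last dose, and nothing in the plan reads a marker-adjusted contrast against the margin.
- **Direction.** A reader might infer that adjustment always shrinks the difference. It does so only in the pure chain. Under the planned true difference of zero, that chain has nothing to shrink. With a direct effect on the marker, a true zero can still be displaced, for example by 0.5 × 11 × 0.5 = 2.75 points at r = 0.5 and c of 0.5 in either direction.
- **The reverse question.** A reader might infer that the link from estradiol to the tissue markers is ignored. Section 13.5 does list an association of estradiol with tissue and circulating biomarkers, and it plans ANCOVA of marker changes by arm. What is missing is a stated direction and estradiol change as a named covariate.
- **Causal order.** The step from estradiol to Ki-67 or PgR is implied by the background, not stated. Section 2.3 calls the role of PgR less clear, at least with tamoxifen, and notes that it may change without treatment.

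What the reply does not answer is that the exploratory label is justified by limited power, and bias from conditioning on a consequence or a duplicate of the outcome is a different problem.

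**Conclusion.** The point holds for Ki-67, PgR, the second estradiol assay and tissue estradiol. For these the analysis as written cannot estimate mediation, and the adjusted arm coefficient cannot be called independent of the marker. In a pure chain the shrinkage is 9%, 25% and 49% for assumed within-arm correlations of 0.3, 0.5 and 0.7. If the schedule reaches the marker by another path, the bias may be larger, smaller or reversed. These sizes rest on correlations and direct effects that the documents do not give, on a linear model, and on no allowance for estradiol values below detection, which Section 13.4 expects to be common. The consequence is confined to the interpretation of an exploratory analysis. The primary comparison, the 6-point margin and the sample size stand.

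**What to change.** Reword Section 13.5 before analysis as follows.

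1. Assign each marker to a class: upstream (serum exemestane and metabolite; leptin or crown-like structures if justified), downstream (Ki-67, PgR) or duplicate measure of estradiol (second assay, tissue estradiol). Where the order of a remaining marker cannot be argued, report association only.
2. Restrict the mediation question on estradiol, without deleting it, to upstream markers measured after randomization.
3. Treat UGT2B17 genotype and baseline adipokines as predictors or effect modifiers. Randomized dose cannot change them, so they cannot be mediators.
4. For Ki-67 and PgR, make marker change the outcome, adjusted for its baseline. Report the arm coefficient without and then with estradiol change. Label this exploratory, and state its limits: unmeasured confounding between estradiol and the marker, and estradiol values below detection.
5. State that marker-adjusted estradiol contrasts will not be read against the 6-point margin.

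The cost is some added wording. No new data are needed. The downside is minor: the reversed model is still a mediation analysis and rests on the assumptions in item 4.
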